In Phase II: The PI will pilot IM Whole by treating 5 Veterans suffering from stroke and comorbid psychological distress. Five Veterans with stroke and comorbid psychological distress will be recruited from the stroke acute care unit, rehabilitation unit, and outpatient stroke follow-up clinic. Qualitative interviews asking the Veterans opinion regarding the treatment content and delivery method will be administered at the end of the final session.

In phase III: Interested Veterans will be randomized to IM Whole (n=15) or usual care plus education (UC+E) (n=15), respectively. Veterans in the UC+E group will receive standard acute care, rehabilitation unit or

outpatient follow-up clinic stroke treatment provided at the MEDVAMC. The standard of care for these patients consists of appointments in the outpatient stroke follow-up clinic, medication management for comorbid chronic diseases, and general physical rehabilitation exercises. To account for additional treatment contact provided to participants in I'm Whole, UC+E will also receive 6 brief telephone calls with information regarding unrelated health topics (e.g., breast, colon, rectal, esophageal, skin and testicular cancer treatment and prevention). We will track the number of patients screened, number and percent of patients eligible, number randomized, number and percent completing treatments, and number and percent completing subsequent follow-up assessments following treatment completion. Veterans in I'm Whole will complete the same qualitative interviews described in phase II.

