## Section G: Sample Size/Data Analysis

### G1. Sample Size

How many subjects (or specimens, or charts) will be used in this study?

Local: 50      Worldwide: 50

Please indicate why you chose the sample size proposed:

Phase I: does not involve participants. We plan to recruit 5 participants for phase II and 30 participants for phase III. To account for a 40% drop out rate the PI evidenced in a prior study using Video telehealth, we will over recruit for phase II and phase III. Recruitment feasibility of approximately 6 subjects per month is based on the number of participants from [name] VSTOP study who also had comorbid psychological distress. The study is underpowered to show clinically meaningful efficacy of *I'm Whole* when compared to usual care.

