### G2. Data Analysis

Provide a description of your plan for data analysis. State the types of comparisons you plan (e.g. comparison of means, comparison of proportions, regressions, analysis of variance). Which is the PRIMARY comparison/analysis? How will the analyses proposed relate to the primary purposes of your study?

We hypothesize that, at 12 weeks posttreatment, Veterans randomized to I2m Whole will show greater improvements in the primary outcome (QoL) and secondary outcomes (PF, physical activity, SRF and psychological distress). On the basis of retention rates for VSTOP trials using VT, we anticipate a 20% loss-to-follow-up rate at 12 weeks post-treatment. Initial analyses will be intention-to-treat. Analyses will be repeated using the observed data (completer analyses). We will run linear regression models. The model for each outcome will include treatment, time (baseline, posttreatment, and 12 weeks post-treatment) and treatment-by-time interaction. Significant interaction will indicate that the intervention groups showed differential improvement over time. We will use SAS PROC MI and PROC MIANALYZE to impute missing data and conduct analyses. Key demographic and clinical variables (e.g., age, gender, stroke, psychological symptom severity and psychotropic medication use) will be described for each group as recommended by the CONSORT statement for RCTs. We will calculate the effect size, d, at post-treatment and at 12 weeks posttreatment, using mean values from the estimated means and standard errors from the linear model analyses of the imputed datasets.

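### G2 treats baseline as a visit instead of adjusting for it, which costs precision at 15 per arm and leaves the effect estimates exposed to chance baseline imbalance

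*Combined protocol and SAP*

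**What the plan says.** Phase III is a small randomized comparison (F1. Design): "Interested Veterans will be randomized to IM Whole (n=15) or usual care plus education (UC+E) (n=15), respectively". For the analysis, G2 states "We will run linear regression models" and then "The model for each outcome will include treatment, time (baseline, posttreatment, and 12 weeks post-treatment) and treatment-by-time interaction". The test is read from the interaction: "Significant interaction will indicate that the intervention groups showed differential improvement over time". The effect size comes from the same fit: "We will calculate the effect size, d, at post-treatment and at 12 weeks posttreatment, using mean values from the estimated means and standard errors".

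No section enters the baseline value of the outcome as a covariate or requires the arms to share a baseline mean. Baseline clinical variables are for description only: "psychological symptom severity and psychotropic medication use) will be described for each group as recommended by the CONSORT statement for RCTs". G2 names no within-person covariance structure. It also does not say whether d is the arm difference at a visit or the arm difference in change to that visit.

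**The concern.** Randomization makes the expected baseline means of the two arms equal. A model with a treatment effect at baseline spends information on estimating a difference known to be zero in expectation. The contrasts behind the interaction test are then differences in raw change, and the estimated means at a follow-up visit carry no correction for where each arm started.

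Section D makes preliminary data on effects one of the study's aims, and G1 concedes that the trial is underpowered for efficacy. What the outcome analysis can offer is therefore an estimate with an interval. With 15 per arm, a sizeable chance difference at baseline is quite likely, and how the model handles it affects both the estimate and its width. The baseline value needed to do better is already being collected.

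**Working it through.** **Inputs.** From the documents: 15 per arm (F1), the model terms, the interaction test and the source of d (G2), and expected losses of 20% (G2, "we anticipate a 20% loss-to-follow-up rate at 12 weeks post-treatment") and 40% (G1, "To account for a 40% drop out rate the PI evidenced in a prior study using Video telehealth"). The documents give no SD and no baseline-to-follow-up correlation (rho), and they state no precision figure to reproduce. Assumed: equal SDs, complete data, rho of 0.3, 0.5 or 0.7. All results are in outcome SD units.

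**Size of chance imbalance.** The SD of the baseline difference is sqrt(2/n).

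- n = 15: sqrt(2/15) = 0.365. The probability that it exceeds 0.5 in either direction is P(|Z| > 0.5/0.365) = 17%.
- n = 12 (15 less 20%): SD 0.408, probability 22%.
- n = 9 (15 less 40%): SD 0.471, probability 29%.
- n = 21 (an assumption, if over-recruitment meant 30 × 1.4 = 42 randomized): SD 0.309, probability about 10%.

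**Response of each estimate to a baseline difference δ.** Given δ, the expected follow-up difference moves by rho·δ. The change contrast moves by rho·δ − δ = −(1 − rho)·δ. The adjusted estimate moves by about 0. For δ = 0.365 and rho 0.3 / 0.5 / 0.7:

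- follow-up means: +0.11 / +0.18 / +0.26
- change contrast: −0.26 / −0.18 / −0.11

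The first two always differ by δ itself. In 20,000 simulated trials at 15 per arm, the slopes on δ were +0.29 / +0.50 / +0.70 for follow-up means, −0.71 / −0.51 / −0.30 for change, and about 0 for the adjusted estimate.

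**Standard errors at 15 per arm.**

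- follow-up means: sqrt(2/15)
- change contrast: sqrt(2/15)·sqrt(2(1 − rho))
- adjusted: sqrt(2/15)·sqrt(1 − rho²)·sqrt(27/26), where the last factor is the small-sample price of estimating the slope with N = 30

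| rho (assumed) | Change contrast | Follow-up means | Adjusted | Variance saved vs change | Variance saved vs follow-up |
|---|---|---|---|---|---|
| 0.3 | 0.432 | 0.365 | 0.355 | 32% | 6% |
| 0.5 | 0.365 | 0.365 | 0.322 | 22% | 22% |
| 0.7 | 0.283 | 0.365 | 0.266 | 12% | 47% |

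The simulated SDs agree to within 0.003. At rho 0.5 the adjusted variance is 0.778 of the planned one, so 30 Veterans give the precision of about 30/0.778 = 39.

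**Edge of the range.** At rho 0.2, follow-up means have the same variance as the adjusted analysis (ratio 1.00), while the change contrast has 1.60 times as much. At rho 0.8 the ratios are 2.67 and 1.07. No value in the range 0.2 to 0.8 makes both planned quantities efficient.

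**Covariance.** The change-contrast figures are sampling SDs. An ordinary regression on stacked visits that ignored the within-person correlation would report about sqrt(4/15) = 0.516 for the same contrast at any rho.

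**The case against.** The planned model is a conventional repeated-measures model. It is unbiased over randomization, and its interaction speaks directly to G2's hypothesis about improvement. The study is a pilot that disclaims efficacy, its feasibility counts and interviews matter as much as d, and no go/no-go rule depends on d. The gain rests on a correlation that the documents do not give. It looks smaller as a standard error (at rho 0.5, from 0.365 to 0.322, about 12%), it was not computed under the planned multiple imputation, and it disappears for follow-up means near rho 0.2.

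Most of this stands, and it sets the weight of the point: this is an efficiency improvement, not an error of validity. It does not remove the gain. Unbiasedness on average does not protect the one trial that is run. Nor does multiple imputation settle the matter, because the analysis model still leaves the baseline means free.

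A reader might go further and infer that d is certainly uncorrected, so that d and the interaction must disagree. G2 does not support that certainty. It says only that d uses estimated means and standard errors; if d is built from the difference in change, it agrees with the interaction contrast. A reader might also infer that imbalance biases the planned estimate. It does not: the shift is conditional on the imbalance that happens to occur.

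**Conclusion.** The point holds as one of precision and of sensitivity to this trial's own baseline imbalance. The interaction contrast over-corrects that imbalance. If d is a difference in follow-up means, it under-corrects and can depart from the contrast by the full imbalance. If d is a difference in change, the two agree and share the loss.

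The sizes are those tabulated above. They rest on equal SDs, complete data, 15 per arm and an assumed rho. The saving against the change contrast is present across the range examined; the saving against follow-up means is negligible at low rho and large at high rho. The change is worth making because it is nearly free, but the planned analysis would not be invalid without it.

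**What to change.** Replace the model sentence in G2 with one of these, for each outcome:

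1. Model the post-treatment and 12-week values with baseline value, treatment, visit, treatment-by-visit and baseline-by-visit, using an unstructured within-person covariance.
2. Keep all three visits with the same covariance structure, but constrain the arms to a common baseline mean.

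The two are close with complete data but not identical when values are missing, so G2 should name one. Fit it within each imputed dataset, and take both the 12-week treatment effect with its interval and d from that single model. State that d is the adjusted difference at the visit, and name the SD that divides it. The residual SD after adjustment is smaller (by a factor sqrt(1 − 0.25) = 0.866 at rho 0.5), so dividing by it would raise d merely because the model changed.

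Cost: a change of wording in G2 and a small change to the SAS model, with no new data. The first form adds one baseline slope per follow-up visit (two parameters). The second uses one parameter fewer than planned.

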## **Section H: Potential Risks/Discomforts**

### **H1. Potential Risks/Discomforts**

Describe and assess any potential risks/discomforts; (physical, psychological, social, legal, or other) and assess the likelihood and seriousness of such risks:

The study will present minimal risks or discomforts. Participants will be asked if they have any psychological distress that may prevented them from fully participating in their stroke self-management treatment. Participants may become mildly uncomfortable with disclosing their psychological distress level and symptoms. However, participants will be reminded that they can discontinue their participation at any time if they feel uncomfortable or feel like their symptoms are getting worse as a result of the treatment. The PI is a licensed psychologist who is able to provide any additional support, symptom assessment, and/or referrals for psychological services that may be needed.

### **H2. Data and safety monitoring plan**

Do the study activities impart greater than minimal risk to subjects?

No

### **H3. Coordination of information among sites for multi-site research**

Is the BCM Principal Investigator acting as the SPONSOR-INVESTIGATOR for this multi-site research?

No or Not Applicable

Is BCM the COORDINATING CENTER for this multi-site research?

No or Not Applicable

## **Section I: Potential Benefits**

Describe potential benefit(s) to be gained by the individual subject as a result of participating in the planned work.

Participants can gain a better understanding of their barriers to healthy eating, physical activity, physical mobility, social engagement, and medication adherence. Understanding and implementing changes to overcome these barriers can lead to improved stroke self-management, decreased stroke risk and improve overall health outcomes.

Describe potential benefit(s) to society of the planned work.

Psychological distress is common among patients who have had a stroke. Increased psychological distress is a predictor of poor mobility and quality of life outcomes post stroke. Thus, it is essential to understand psychological distress barriers to healthy engagement in stroke self-management behaviors. This information should be used to incorporate psychological distress treatment into evidenced based stroke self-management interventions to improve health outcomes among persons at high risk for secondary stroke and related chronic disease. Successful findings can lead to the development and implementation of a comprehensive treatment that addresses stroke self-management and psychological distress concurrently. This can have widespread public health implications given the high prevalence rate of stroke and comorbid psychological distress.

Stroke patients with co morbid mental illness have more outpatient visits and withdraw from family and community activities more due to psychological symptoms than stroke patients that are not suffering from comorbid mental illness. Better stroke management can lead to increased family and community involvement and over all quality of life as a result.

Do anticipated benefits outweigh potential risks? Discuss the risk-to-benefit ratio.

Having a better understanding of psychological distress barriers to making healthy stroke self-management choices will have greater benefits and outweigh potential risks.

## **Section J: Consent Procedures**

### **J1. Waiver of Consent**

Will any portion of this research require a waiver of consent and authorization?

Yes

Please describe the portion of the research for which a waiver is required. (Example: chart review to determine subject eligibility)

A preliminary chart review will be conducted for interested study participants to examine if they have been hospitalized for psychiatric reasons within the last 30 days and if they have a diagnosis of psychotic or bipolar disorder to ensure study eligibility. A waiver of consent and HIPAA authorization is requested to determine subject eligibility.

An additional waiver of HIPPA authorization is being requested for the entire study for the following reason: To reduce participant burden, verbal consent is being obtained for study participation (see request to waive written documentation of consent in J1a). Therefore, we request a waiver of the requirement for HIPPA authorization for study participation.

Explain why the research and the use or disclosure of protected health information involves no more than minimal risk (including privacy risks) to the individuals.

The research involves no more than minimal risk to the participants because the waiver will not affect the rights and welfare of the potential participants as this knowledge will be gained from medical records which can be accessed widely by VA researchers and clinicians. The only information reviewed in the medical records is that which will have already been asked of the patients. The patient will also be informed the research staff will review their medical records for the inclusion/exclusion criterial only.

The examination will be limited to mental health diagnosis, coexisting medical conditions, hospitalization for psychiatric, substance and/or alcohol use within the last 30 days. This information would have already been shared with the patient. Also, the data will not be used for any clinical purposes but only to determine eligibility for the current study. The purpose of collecting information covered under U.S.C 7332 is to conduct scientific research and no personnel involved in this study will identify, directly or indirectly, any individual patient or subject in any report of such research."

Explain why the waiver will not adversely affect the privacy rights and the welfare of the research subjects.

The waiver or alteration will not adversely affect the rights and welfare of the subjects, because the waiver will not affect the privacy rights and welfare of the potential participants as this knowledge will be gained from a medical records which can be accessed widely by VA researchers. The medical records information reviewed by the research staff that has already been shared with the patients and does not include undisclosed health information. The medical records examination will be limited to mental health diagnosis, coexisting medical conditions, hospitalization for psychiatric within the last 30 days. This information would have already been shared with the patient. Also, the data will not be used for any clinical purposes but only to determine eligibility for the current study.

Explain why the research could not practicably be conducted without the waiver and could not practicably be conducted without access to and use of the protected health information.

The research could not practicably be carried out without the waiver or alteration and without access to and use of the requested information, because conducting this initial medical chart investigation is essential to the research project. After experiencing a stroke, Veterans can experience a varying level of psychological distress and may have pre-existing psychological distress. Our program is not suited for participants with severe psychological distress. It would not be feasible to rely solely use the statements of the participant to gauge inclusion and exclusion criteria given patients with prior psychological distress may be more focused on the physical aspects of their stroke rather than their prior psychological symptoms. A greater focus on their physical changes may impact accurate recall of past information.

Describe how the research could not practicably be carried out without using the collected identifiable biospecimens in an identifiable format.

NA

Describe how an adequate plan exists in order to protect identifiers from improper use and disclosure.

An adequate plan exists in order to protect health information identifiers from improper use and disclosure, because all gathered PHI for potential participants will be stored in a locked file cabinet in a locked data storage room behind the VA firewall. No one outside of the PI, PI's research coordinator, Baylor College of Medicine Institutional Review Board members, VA Research and Development office and research compliance officers will have access to the data or limited PHI information.

Describe how an adequate plan exists in order to destroy identifiers at the earliest opportunity consistent with conduct of the research, unless there is a health or research justification for retaining the identifiers or such retention is otherwise required by law.

An adequate plan exists in order to destroy identifiers at the earliest opportunity consistent with conduct of the research (absent a health or research justification for retaining them or a legal requirement to do so), because the information will be de-identified during the data entry process. The de-identified information will be used during all statistical analysis. The de-identified data will be stored in an encrypted file on the VA server. All of the identifiable and de-identified data (VA consent and HIPPA forms and audio files) will be properly destroyed immediately at the conclusion of the research project using VA established regulations. Research records, including identifiers will be destroyed 6 years after cutoff (at the end of the fiscal year) after completion of the research project, but may be retained longer if required by other federal regulations or sponsor archive requirement.

Describe how adequate written assurances exist in order to ensure that the PHI will not be reused or disclosed to (shared with) any other person or entity, except as required by law, for authorized oversight of the research study, or for other research for which the use or disclosure of the PHI would be permitted under the Privacy Rule.

Adequate written assurances exist in order to ensure that the PHI will not be reused or disclosed to (shared with) any other person or entity, except as required by law, for authorized oversight of the research study, or for other research for which the use or disclosure of the PHI would be permitted under the Privacy Rule, because all gathered PHI for potential participants will be stored in a locked file cabinet in a locked data storage room behind the VA firewall. No one outside of the PI, PI's research coordinator, Baylor College of Medicine Institutional Review Board members, VA Research and Development office and research compliance officers will have access to the data or limited PHI information

Information from health records such as diagnoses, progress notes, medications, lab or radiology findings, etc.

Yes

Specific information concerning alcohol abuse:

Yes

Specific information concerning drug abuse:

Yes

Specific information concerning sickle cell anemia:

No

Specific information concerning HIV:

No

Specific information concerning psychiatry notes:

Yes

Demographic information (name, D.O.B., age, gender, race, etc.):

Yes

Full Social Security #:

No

Partial Social Security # (Last four digits):

Yes

Billing or financial records:

No

Photographs, videotapes, and/or audiotapes of you:

Yes

Other:

No

Will additional pertinent information be provided to subjects after participation?

No

If No, explain why providing subjects additional pertinent information after participation is not appropriate.

Providing participants additional pertinent information after participation is not appropriate, because this information has already been shared with the participant by other clinicians. All additional information gained from the additional assessments and semi-structured interviews will be provided by the patient. Thus, there will not be any new information gained that the participant will not already know or have provided

